6.1.1 Investigation of Hysteresis

Hysteresis will be assessed based on joint graphical displays of the least squares (LS) mean $\Delta\Delta\text{QTcF}$ at each post-baseline time point from the by-time point analysis and the mean concentrations of CBP-307 at the same time points. In addition, hysteresis loops will be given for LS mean $\Delta\Delta\text{QTcF}$ from the by-time point analysis and the mean concentrations. Other concentration-QTc models such as a model with an effect compartment may be explored if all of the following 3 conditions are met.

- A QT effect ≥ 10 ms (i.e., LS mean $\Delta\Delta\text{QTcF} \geq 10$ ms) cannot be excluded in the by-time point analysis in the CBP-307 dose groups on Days 6 and 15
- The mean peak $\Delta\Delta\text{QTcF}$ effect is observed at the same post-dose time point in the by-time point analysis in the CBP-307 dose groups on Days 6 and 15
- The difference (delay) between the time to reach the peak QTc effect ($\Delta\Delta\text{QTcF}$) and T_{\max} is larger than 1 hour in a consistent way in the CBP-307 dose groups on Days 6 and 15

With the provision stated above, hysteresis will be demonstrated if the curve of the hysteresis plot shows a counterclockwise loop. A significant treatment effect-specific intercept may also be indicative of hysteresis or model misspecification, if it cannot be explained by a nonlinear relationship.

6.1.2 Appropriateness of a Linear Model

To assess the appropriateness of a linear model, normal quantile-quantile (Q-Q) plots for the standardized residuals and the random effects will be produced. Scatter plots of standardized residuals versus concentration, versus model fitted values of ΔQTcF , and versus centered baseline QTcF (if available) will also be produced, as well as box plots of standardized residuals versus nominal time, and versus CBP-307 treatment. Among these plots, the scatter plots of standardized residuals versus concentration, and versus centered baseline QTcF (if available) will include the locally weighted scatter plot smoothing (LOESS, Cleveland³) line with an optimal smoothing parameter selected by the Akaike information criterion with a correction (AICC). (Hurvich et al⁴). A scatter plot of observed concentration and ΔQTcF with a LOESS smooth line with 90% CI and a linear regression line will also be provided to check the assumption of a linear concentration-QTc relationship. If there is an indication that a linear model is inappropriate, additional models may be fitted, specifically an E_{\max} model. The concentration-QTc analysis will then be repeated for the model found to best accommodate the nonlinearity detected.

6.2 Assay Sensitivity

The analysis to show assay sensitivity will be based on the concentration-QTc analysis of the effect on $\Delta\Delta\text{QTcF}$ of 400 mg oral moxifloxacin using a similar model as for the primary analysis. That is, the relationship between moxifloxacin plasma concentration and ΔQTcF will be investigated by linear mixed-effects modeling. The model will include ΔQTcF as the dependent variable, moxifloxacin plasma concentration as the explanatory variable (0 for placebo), study treatment (1 for moxifloxacin and 0 for placebo) and time (i.e., post-baseline time point on Day 1

as defined in Table 4 for each period) as fixed effects, and random effects on intercept and slope per subject (Garnett et al¹). Centered baseline QTcF will be included in this model as an additional covariate. If necessary, a sensitivity analysis will be performed using the model without this term. The geometric mean of the individual C_{max} values for subjects receiving the single dose of 400 mg moxifloxacin will be determined. The predicted effect and its 2-sided 90% CI for $\Delta\Delta QTcF$ (i.e., slope estimate \times concentration + treatment effect-specific intercept) at this geometric mean C_{max} will be obtained.

If the slope of the moxifloxacin plasma concentration/ $\Delta QTcF$ relationship is statistically significant at the 10% level in a 2-sided test and the lower bound of the 2-sided 90% CI of the predicted QT effect at the observed geometric C_{max} of the 400 mg dose is above 5 ms, assay sensitivity will be deemed to have been demonstrated.

The SAS code for the concentration-QTc analysis is as follows.

```
PROC MIXED DATA=PKPD method=reml;
CLASS SUBJID TIME;
MODEL DQTc=TRT CONC TIME CBASE / solution cl noint alpha=0.1 alphap=0.1 COVB DDFM=KR;
RANDOM INT CONC /TYPE=UN SUBJECT=SUBJID s;
ESTIMATE 'Pred Mean Diff for T7' TRT 1 CONC &GeoMeanCmax_1 / CL ALPHA=0.1;
RUN;
```

Where PKPD = PK/QTc population, SUBJID = subject number, TRT = treatment (1 for moxifloxacin = 1 and 0 for placebo), TIME = nominal post-baseline time point on Day 1, CONC = plasma concentration of moxifloxacin, CBASE = centered baseline QTcF, T7 = moxifloxacin group, GeoMeanCmax_1 = geometric mean C_{max} for T7, DQTc = $\Delta QTcF$.

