5.3 Baseline

Baseline for the assessment of the ECG effect of CBP-307 (CBP-307 in Group 1 versus placebo in Groups 2A and 2B) will be time-matched values on Day -1 ([Table 3](#)).

For assay sensitivity in Groups 2A and 2B, the following baselines will be used:

- Group 2A: For moxifloxacin administered on Day 1 (defined as Period 1 Day 1), baseline will be Day 16 (defined as Period 1 Day -1), on which subjects are administered placebo. For placebo-correction in this group, placebo values will be derived from Day 15 (defined as Period 2 Day 1) on which subjects are administered placebo, and baseline will be obtained on Day -1 (defined as Period 2 Day -1).
- Group 2B: For moxifloxacin administered on Day 16 (defined as Period 2 Day 1), baseline will be Day 1 (defined as Period 2 Day -1), on which subjects are administered placebo. For the placebo-correction in this group, Day -1 (defined as Period 1 Day 1) values will be used as placebo (no treatment) and baseline will be obtained on Day 15 (defined as Period 1 Day -1).

For T-wave morphology and U-wave presence, baseline includes findings observed in any replicates from all time points that constitute baseline.

Table 3 Treatment administration and baseline definition

Day	Treatment Arm Group 1	Control Arm	
		Group 2A	Group 2B
-1	CBP-307 placebo Baseline for T1, T2, T3	CBP-307 placebo Baseline for T5 and T6; Baseline for T8 moxifloxacin- placebo on Day 15	CBP-307 placebo Baseline for T4, T5 and T6; T8: moxifloxacin-placebo on Day -1;
1	CBP-307 0.05 mg Moxifloxacin-placebo T1: CBP-307 0.05 mg on Day 1	400 mg Moxifloxacin CBP-placebo T7: moxifloxacin on Day 1	Moxifloxacin-placebo CBP-placebo T4: corresponding placebo on Day 1; Baseline for T7 on Day 16
6	CBP-307 0.2 mg T2: CBP-307 0.2 mg on Day 6	CBP-307-placebo T5: corresponding placebo on Day 6	CBP-307-placebo T5: corresponding placebo on Day 6
15	CBP-307 0.5 mg T3: CBP-307 0.5 mg on Day 15	CBP-307-placebo T6: corresponding placebo on Day 15 T8: moxifloxacin-placebo on Day 15	CBP-307-placebo T6: corresponding placebo on Day 15; Baseline for T8 moxifloxacin- placebo on Day -1
16	CBP-307 placebo Moxifloxacin-placebo (not analyzed)	CBP-307 placebo Moxifloxacin-placebo Baseline for T7 on Day 1	CBP-307 placebo 400 mg Moxifloxacin T7: moxifloxacin on Day 16

Note: To facilitate analysis, the nested crossover design for the moxifloxacin/placebo comparison for assay sensitivity needs to be coded following a 2-period crossover study design

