6.1 Concentration- QTc Analysis (Primary Analysis)

The relationship between CBP-307 plasma concentrations and change-from-baseline $QTcF$ ($\Delta QTcF$) will be quantified using a linear mixed-effects modeling approach with $\Delta QTcF$ as the dependent variable, time-matched concentrations of CBP-307 as the exploratory variate (0 for placebo), treatment (active=1 or placebo=0), and time (i.e., post-baseline time points on Days 1, 6, and 15: categorical) as fixed effects, and a random intercept and slope for concentrations per subject (Garnett et al¹). Centered baseline $QTcF$ (i.e., baseline $QTcF$ for individual subject minus the population mean baseline $QTcF$ for all subjects) will be included in this model as an additional covariate. If necessary, a sensitivity analysis will be performed using the model without this term. CBP-307 plasma concentrations below the quantifiable limit at pre-dose will be set to zero and after dosing will be set to 1/2 the lower limit of quantitation in the concentration- QTc analysis.

An unstructured covariance matrix will be specified for the random effects. If convergence cannot be achieved even after appropriate rescaling of the concentrations, the random effect on the slope and intercept will be dropped, in this order, until convergence is achieved. The degrees of freedom of estimates will be determined by the Kenward-Roger method. From the model, the slope (i.e., the regression parameter for concentration) and the treatment effect-specific intercept

(defined as the difference between CBP-307 and placebo) will be estimated together with the 2-sided 90% CI. The estimates for the time effect will be reported with degrees of freedom and SE.

For the assessment of the ECG effect of CBP-307 versus placebo, the time term incorporated into the models (both by-time point analysis and concentration-QTc analysis [or assay sensitivity]) includes the single pre-dose time point and all post-dose time points on Days 1, 6, and 15, and Days 1 and 16 for active versus placebo and moxifloxacin versus placebo, respectively. All times are relative to the time of dosing on that day which is considered the first dose for the assay sensitivity analysis. For the analysis of CBP-307 versus placebo, the first dose of study treatment is on Day 1.

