6.3 By-Time Point Analysis

The by-time point analysis for QTcF will be performed for CBP-307 versus placebo. A linear mixed-effects model will be used with $\Delta QTcF$ as the dependent variable and time (i.e., post-baseline time point on Days 1, 6, and 15: categorical), treatment (therapeutic dose of CBP-307 on Day 1, therapeutic dose of CBP-307 on Day 6, supratherapeutic dose of CBP-307 on Day 15, and corresponding placebo), and time-by-treatment interaction as fixed effects. Baseline QTcF will be included in this model as an additional covariate. If necessary, a sensitivity analysis will be performed using the model without this term. An unstructured covariance matrix will be specified for the repeated measures at post-baseline time points within subjects. If the model with an unstructured covariance matrix fails to converge, this by-time point analysis will be performed by day separately, and other covariance matrices such as compound symmetry and autoregressive will be considered, in this order, until convergence is achieved. From this analysis, the LS mean, SE, and 2-sided 90% CIs will be calculated for the contrast “CBP-307 versus placebo” at each post-baseline time point on Days 1, 6, and Day 15, respectively.

The by-time point analysis for QTcF will be also performed for moxifloxacin versus placebo at post-baseline time points on Day 1 (as defined in Table 4 for each period). A linear mixed-effects model will be used with $\Delta QTcF$ as the dependent variable and time (i.e., post-baseline time points on Day 1: categorical), treatment (moxifloxacin and placebo), period (as defined in Section 5.3 and illustrated in Table 4), sequence (placebo/moxifloxacin or moxifloxacin/placebo), and time-by-treatment interaction as fixed effects. Baseline QTcF will be

included in this model as an additional covariate. If necessary, a sensitivity analysis will be performed using the model without this term. An unstructured covariance matrix will be specified for the repeated measures at post-baseline time points for subject within period. The model will also include a subject-specific random effect. If the model with an unstructured covariance matrix fails to converge, other covariance matrices, such as compound symmetry or autoregressive, will be considered. From this analysis, the LS mean, SE, and 2-sided 90% CIs will be calculated for the contrast “moxifloxacin versus placebo” at each post-baseline time point on Day 1, respectively.

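### The concentration-QTc model that decides assay sensitivity has no PERIOD term, although the Table 4 relabelling turns any QTc drift over the stay into a period effect

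*SAP*

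**What the plan says.** All references are to the cardiodynamic SAP.

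- **Relabelling (Section 5.3, Table 4).** Groups 2A and 2B are coded as a two-period crossover. For moxifloxacin on Day 1 in Group 2A, "baseline will be Day 16 (defined as Period 1 Day -1"), so the baseline day comes 15 days after the analysed day. The 2A placebo change is Day 15 against Day -1. In Group 2B, moxifloxacin on Day 16 is set against Day 1, and the placebo day is Day -1 with Day 15 as its baseline.
- **Deciding model (Section 6.2).** Assay sensitivity is analysed "using a similar model as for the primary analysis". The code is "CLASS SUBJID TIME", then "MODEL DQTc=TRT CONC TIME CBASE / solution cl noint alpha=0.1 alphap=0.1 COVB DDFM=KR", then "RANDOM INT CONC /TYPE=UN SUBJECT=SUBJID s". The text lists the same fixed effects. The only variant planned drops the centred baseline, and only if needed.
- **Decision rule (Section 6.2).** The concentration slope must be significant at the two-sided 10% level, and the lower 90% bound at the geometric mean Cmax must exceed 5 ms.
- **By-time-point model on the same data (Section 6.3).** Its fixed effects include "period (as defined in Section 5.3 and illustrated in Table 4), sequence (placebo/moxifloxacin or moxifloxacin/placebo").

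**The concern.** The primary CBP-307 comparison is between parallel groups and has no periods. Carrying its model over to moxifloxacin leaves out a term that the crossover recoding makes necessary. TIME cannot stand in for it: Section 6.2 defines "TIME = nominal post-baseline time point on Day 1", so the same levels occur in both relabelled periods. A random intercept per subject cannot either, because drift has opposite signs in a subject's two periods. What drift remains goes into the residual and the random-slope variance, and from there into the interval compared with 5 ms. No reason is given for leaving PERIOD out of one moxifloxacin model while including it in the other.

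**Working it through.** **1. The plan's own sizing (Section 6.6) reproduces.** The reference SE of 1.24 ms with 24 subjects implies an SD of the test variable of 1.24 × √24 = 6.07 ms. The effect size is (10 - 5)/6.07 = 0.82. A paired t-test with n = 28 at one-sided 5% has power 95.1% at effect size 0.64 and 99.5% at 0.82. The tolerable within-subject SD is 5.4 × 0.82/0.64 = 6.9 ms.

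**2. Drift under Table 4.** Let QTc on Days 15 and 16 be D ms higher than on Days -1 and 1, equally for all subjects.

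| Group | Relabelled period | Treatment | Change | Drift |
|---|---|---|---|---|
| 2A | 1 | moxifloxacin | Day 1 - Day 16 | -D |
| 2A | 2 | placebo | Day 15 - Day -1 | +D |
| 2B | 1 | placebo | Day -1 - Day 15 | -D |
| 2B | 2 | moxifloxacin | Day 16 - Day 1 | +D |

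Drift depends on period alone, and the two periods differ by 2D. Within each sequence it sums to zero, so SEQUENCE does not capture it. The moxifloxacin-minus-placebo difference moves by -2D in 2A and +2D in 2B.

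**3. Equal evaluable numbers (14/14).** The shifts cancel in the mean but remain in the estimated variance:

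SE without PERIOD = √[(6.07² + 4D² × 28/27)/28]; SE with PERIOD = 6.07/√28 = 1.15 at every D.

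For D = 3: √[(36.9 + 37.3)/28] = 1.63. Power is from 200,000 simulated trials with a true effect of 10 ms.

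| D (ms, assumed) | SE without PERIOD | 90% half-width | Power |
|---|---|---|---|
| 0 | 1.15 | 1.96 | 99.5% |
| 2 | 1.38 | 2.35 | 98.8% |
| 3 | 1.63 | 2.77 | 97.0% |
| 4 | 1.92 | 3.27 | 92.8% |
| 5 | 2.24 | 3.82 | 84.2% |

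With PERIOD the half-width stays at 1.96 ms and power at 99.5% throughout.

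**4. Unequal evaluable numbers.** Without PERIOD, bias = 2D(n2B - n2A)/n. For 17 in 2A and 13 in 2B at D = 3: 6 × (-4)/30 = -0.8 ms. For 11 in 2A and 17 in 2B at D = 4: 8 × 6/28 = +1.7 ms. Simulated fits of the mixed model gave about -0.4 ms in the first case, so the formula is better read as an approximate upper limit.

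**5. The mixed model itself.** The paired frame ignores the centred baseline, which can take up part of the drift because the baseline also shifts by D between periods. Fits to simulated trials (60 per setting, assumed variances) gave these SEs at 14/14:

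- D = 3: 1.20 ms as planned, against a sampling SD of 0.91; 1.07 with PERIOD.
- D = 3 without the baseline covariate: 1.70 against 1.10; 1.12 with PERIOD.
- D = 4, under other assumed variances: 1.92 against 1.04; 1.28 with PERIOD and SEQUENCE.
- No drift, same variances as for D = 4: 1.32 with or without the terms.

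The share absorbed depends on the assumed variances. In another set of runs the planned SE at D = 3 was 1.17 against 1.12 with PERIOD and SEQUENCE, almost no loss. These figures are rough. The model that drops the baseline covariate loses this protection.

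**The case against.** The strongest reply is that the decision would rarely change. The assumed effect of 10 ms stands 5 ms above the threshold. At D = 3 the expected lower bound in the paired frame is 10 - 2.77 = 7.2 ms, and power of 97.0% still exceeds the plan's 95%. Power falls below 95% only somewhere between 3 and 4 ms of drift, and the documents give no ground for expecting that much. With equal numbers the error is conservative, and Section 6.6 randomizes 17 to each subgroup. All of this stands, and it limits the weight of the point. It does not explain the omission.

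A reader might infer more than the documents support:

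- **That drift generally biases the moxifloxacin estimate or could falsely establish assay sensitivity.** With equal evaluable numbers it does neither. Bias needs unequal numbers; its sign then depends on the direction of drift and on which subgroup is smaller.
- **That both periods use reversed baselines.** Only relabelled Period 1 has its baseline after the analysed day. It is the opposite direction of the two periods that creates the effect.
- **That SEQUENCE is needed too.** Drift cancels within each sequence.
- **That two different moxifloxacin models are a fault in themselves.** A concentration slope model and a repeated-measures model differ by design.
- **That the time term is undefined.** Section 6.1 gives "Days 1 and 16 for active versus placebo and moxifloxacin versus placebo, respectively", which does not fit placebo rows taken from Days 15 and -1. But Section 6.2 defines time as relabelled Day 1 of each period, so the Section 6.1 phrase is only loose wording.

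**Conclusion.** The omission is real and follows from Table 4 and the Section 6.2 code without any assumption about variances. Its effect is conditional on drift, which the documents do not quantify; the 0 to 5 ms range is assumed, as is drift that is additive and common to all subjects. If drift is 3 ms or less, the loss is mainly precision and the pass/fail result would seldom change. At 4 to 5 ms the chance of wrongly failing assay sensitivity becomes material, less any part that the baseline covariate absorbs. Unequal evaluable numbers in 2A and 2B add a bias of either sign. This is a worthwhile improvement to an interval that carries a pass/fail rule. It is not evidence that the planned analysis would give a wrong conclusion.

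**What to change.** In Section 6.2, add PERIOD as defined in Table 4 to the list of fixed effects in the text and to the CLASS and MODEL statements, and keep it in the variant without the baseline covariate. SEQUENCE may be added for consistency with Section 6.3 but is not needed for this purpose. The ESTIMATE statement for the predicted effect can stay as it is. The placebo-adjusted values plotted for moxifloxacin under Section 5.5 should then have the estimated period effect removed along with the time effect.

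As a minor edit, align the moxifloxacin part of the time-term sentence in Section 6.1 with the Section 6.2 definition.

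The cost is about one degree of freedom and a few lines of text and code. No new data are needed, and in the simulated fits the SE was unchanged when there was no drift.

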6.3 By-Time Point Analysis

The by-time point analysis for QTcF will be performed for CBP-307 versus placebo. A linear mixed-effects model will be used with $\Delta QTcF$ as the dependent variable and time (i.e., post-baseline time point on Days 1, 6, and 15: categorical), treatment (therapeutic dose of CBP-307 on Day 1, therapeutic dose of CBP-307 on Day 6, supratherapeutic dose of CBP-307 on Day 15, and corresponding placebo), and time-by-treatment interaction as fixed effects. Baseline QTcF will be included in this model as an additional covariate. If necessary, a sensitivity analysis will be performed using the model without this term. An unstructured covariance matrix will be specified for the repeated measures at post-baseline time points within subjects. If the model with an unstructured covariance matrix fails to converge, this by-time point analysis will be performed by day separately, and other covariance matrices such as compound symmetry and autoregressive will be considered, in this order, until convergence is achieved. From this analysis, the LS mean, SE, and 2-sided 90% CIs will be calculated for the contrast “CBP-307 versus placebo” at each post-baseline time point on Days 1, 6, and Day 15, respectively.

The by-time point analysis for QTcF will be also performed for moxifloxacin versus placebo at post-baseline time points on Day 1 (as defined in Table 4 for each period). A linear mixed-effects model will be used with $\Delta QTcF$ as the dependent variable and time (i.e., post-baseline time points on Day 1: categorical), treatment (moxifloxacin and placebo), period (as defined in Section 5.3 and illustrated in Table 4), sequence (placebo/moxifloxacin or moxifloxacin/placebo), and time-by-treatment interaction as fixed effects. Baseline QTcF will be

included in this model as an additional covariate. If necessary, a sensitivity analysis will be performed using the model without this term. An unstructured covariance matrix will be specified for the repeated measures at post-baseline time points for subject within period. The model will also include a subject-specific random effect. If the model with an unstructured covariance matrix fails to converge, other covariance matrices, such as compound symmetry or autoregressive, will be considered. From this analysis, the LS mean, SE, and 2-sided 90% CIs will be calculated for the contrast “moxifloxacin versus placebo” at each post-baseline time point on Day 1, respectively.

For HR, PR, QRS intervals, the analysis will be based on the change-from-baseline post-dosing values (Δ HR, Δ PR, and Δ QRS). The same (by-time point analysis) model will be used as described for QTcF. The LS mean, SE, and 2-sided 90% CI from the statistical modeling for both change-from- baseline and placebo-corrected change-from-baseline values will be listed in the tables and graphically displayed.

The SAS code for the by-time point analysis for QTcF for CBP-307 versus placebo is as follows.

```
PROC MIXED DATA=ECG;
CLASS SUBJID TREAT TIME;
MODEL DQTc=TREAT TIME TREAT*TIME BASE/DDFM=KR;
REPEATED TIME / SUBJECT = SUBJID type = UN;
LSMEANS TREAT*TIME/CL DIFF ALPHA=0.1;
RUN;
```

Where ECG = QT/QTc population, SUBJID = subject number, TREAT = treatment (dose of CBP-307 on Day 1, on Day 6, and on Day 15, and corresponding placebo), TIME = nominal post-baseline time point, BASE = baseline QTcF, and DQTc = Δ QTcF.

The SAS code for the by-time point analysis for QTcF for moxifloxacin versus placebo is as follows.

```
PROC MIXED DATA=ECG;
CLASS SUBJID TREAT TIME PERIOD SEQUENCE;
MODEL DQTc=TREAT TIME TREAT*TIME PERIOD SEQUENCE BASE/DDFM=KR;
RANDOM INTERCEPT / SUBJECT =SUBJID TYPE=UN;
REPEATED TIME / SUBJECT = PERIOD*SUBJID TYPE = UN;
LSMEANS TREAT*TIME/CL DIFF ALPHA=0.1;
RUN;
```

Where ECG = QT/QTc population, SUBJID = subject number, TREAT = treatment (moxifloxacin and placebo), TIME = nominal post-baseline time point, PERIOD= period, SEQUENCE = sequence, BASE = baseline QTcF, and DQTc = Δ QTcF.

